Assessing Neuroinflammation in Gulf War Illness with Whole-
Brain Magnetic Resonance Spectroscopy

Study Protocol & Statistical Analysis Plan

NCT04638998

December 20, 2023

[name], Principal Investigator
University of Alabama at Birmingham
Birmingham, AL 35294

Study Protocol:

Overall design

This observational neuroimaging study uses a 3D MRSI sequence to measure several neuroinflammatory markers across the entire brain. A cross-sectional approach is used to contrast 20 veterans with GWI from 20 veterans who were deployed to the Persian Gulf but never presented with symptoms of GWI. Participants will attend a single neuroimaging session.

Participants

GWI group: GWI participants will be men who meet the Kansas GWI diagnostic criteria. CDC criteria will also be assessed, but not used for inclusion purposes. Our primary pool of participants will come from our existing database of individuals who have completed our online, phone, and in-person screening package for GWI eligibility.

Healthy control group: We have a database of individuals who served in Operation Desert Storm and do not present with symptoms of GWI. Individuals will be within the same age and body mass index range as the GWI group.

Screening

Individuals (GWI or healthy) will be excluded for any of the following reasons: Participants cannot be taking experimental medications, opioid analgesics, psychostimulants (except caffeine), or benzodiazepines. Participants cannot have major cardiovascular illness, cancer, or have any contraindications for MRI (including metallic implants or claustrophobia).

Laboratory visits

Participants will undergo venous blood draw at the UAB Clinical Research Unit. The neuroimaging visit will occur at the University of Alabama at Birmingham (UAB) Civitan International Neuroimaging Laboratory, in Highlands Hospital. Body temperature measurements will be taken using a Braun Pro 4000 ThermoScan aural thermometer. Self-report instruments will then be completed. Participants will then undergo scanning on a 3T Siemens Magnetom Prisma scanner with a 20-channel head coil, which will take approximately one hour. Last, participants will be debriefed and paid.

Neuroimaging sequences

T1-weighted high-resolution structural scan (5 minutes): For spatial registration, we will use a magnetization-prepared rapid gradient echo (MPRAGE) sequence with 224mm FOV, 320 x 320 matrix, 2400ms TR, 2.15ms TE, 0.9mm slice thickness, and no gap, yielding a 0.9 x 0.9 x 0.9mm 3D image of the brain. The MPRAGE sequence uses a longer TR than traditional ISPGP scans. Our sequences are based on the Human Connectome Project settings recommended for multi-site projects.

Whole-brain MRSI scan (20 min with shimming): The MRSI acquisition will use a whole brain 3D spectroscopic sequence, which acquires the metabolite and water signals in one TR using echo-planar readout. The acquisition will use the following parameters: FOV of 280mm in-plane and 180mm in the inferior-superior direction to yield 5.6x5.6x10mm voxels, 1710ms TR1, 591ms TR2, 17.6ms TE. Signals from subcutaneous lipids will be reduced using an inversion-recovery preparation with inversion time (TI) of 198ms and a saturation band placed across the lipid

region behind the eyes to suppress movement aliasing. A double echo steady state (DESS) pulse sequence will be applied prior to the scan in order to estimate the field. A dynamic shim using higher order coils will optimize the homogeneity of the B0 field and improve spectral resolution; data will be acquired using a full width at half maximum (FWHM) of the water peak at <25Hz.

Arterial spin labeling cerebral perfusion scan (7 min): This scan will be used to rule out the hypo-perfusion contribution to metabolite concentrations and temperature. A 2D ASL scan will be acquired using a Proximal Inversion with Control of Off-Resonance Effects (PICORE) labeling scheme for background suppression. 60 pairs of label/control ASL images will be collected in the axial direction at a single inversion time of 1800 ms, TR=2500 ms, TE=16.18 ms, 12 slices, 4×4×10 mm voxels. Data will be processed using ASLtbx, which works on the basis of SPM12 within MATLAB. Images will be motion-corrected then co-registered to the T1 image and smoothed with a 6mm full-width-at-half-maximum (FWHM) kernel to decrease noise. Each tag/control pair will be subtracted to create 60 perfusion-weighted images used to calculate cerebral blood flow (ml/100g/min).

Statistical Analysis Plan:

Univariate, independent samples t-tests will be used to test for group differences for each brain marker \times ROI combination. The dependent variable will be each of the five neuroinflammatory outcomes and the main predictor of interest is group (GWI vs healthy). A total of 47 brain areas will be tested. Cortical and cerebellum averages will also be computed as a ‘whole brain average’. To compute power, we used the preliminary results from the CFS versus healthy control data. The average significant differences between groups in that study had an effect size (Cohen’s d) of 0.922. Power calculations were performed using G*Power 3.1.9.2. Using the means and standard deviations from that study, we would expect to have a power of 0.81 to detect GWI versus control differences with a statistical threshold of 0.05 and 20 individuals per group. Because this is a Discovery study with a limited sample size, we are not able to set a more restrictive statistical threshold to correct for multiple comparisons. We will report differences that are significant at $p < 0.05$; however, we will use a false-discovery-rate (FDR) adjusted p-value of < 0.0078 to identify differences that are most likely to be replicable. This process should provide an acceptable balance between false positives and negatives in an exploratory study.

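### ROI metabolite values are compared by t-test with no planned check on tissue composition, so a group difference in CSF or grey-matter fraction could appear as a neuroinflammatory one

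*Combined protocol and SAP*

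**What the plan says.** **T1 scan.** In Study Protocol, Neuroimaging sequences, the structural scan is introduced with "For spatial registration, we will use a magnetization-prepared rapid gradient echo (MPRAGE) sequence". The only other mention of the T1 image is in the perfusion paragraph: "Images will be motion-corrected then co-registered to the T1 image". Both uses are registration.

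**Spectroscopy.** The same section gives the MRSI resolution: "FOV of 280mm in-plane and 180mm in the inferior-superior direction to yield 5.6x5.6x10mm voxels". It describes acquisition, lipid suppression and shimming. It does not describe spectral quantification, how the markers are expressed, or any handling of tissue type.

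**Perfusion.** An arterial spin labeling scan is included to exclude reduced perfusion as an explanation for metabolite and temperature findings. Its processing is described down to the toolbox and the smoothing kernel.

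**Analysis.** The Statistical Analysis Plan states: "Univariate, independent samples t-tests will be used to test for group differences for each brain marker", by ROI. On outcomes it says: "The dependent variable will be each of the five neuroinflammatory outcomes". On regions: "A total of 47 brain areas will be tested". Averages for cortex and cerebellum are added. Group is called the main predictor of interest, and no other predictor is named.

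**Design.** Under Participants and Screening, both groups served in the Gulf, controls fall in the same age and body mass index range as cases, and major cardiovascular illness and cancer are excluded.

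**The concern.** A voxel of this size can hold grey matter, white matter and CSF together. If a marker is expressed as a concentration, CSF in the voxel dilutes it. If metabolite levels differ between grey and white matter, the mix of the two also moves the value. Averaging voxels over an ROI reduces random error but leaves a systematic group difference in composition in place.

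The comparison is observational, so nothing in the design balances tissue composition directly. If one group has more CSF or less grey matter in a region, the t-test attributes the resulting shift to group, and the report would call it a neuroinflammatory difference. The same mechanism could hide a real difference, depending on which group has more CSF. A diffuse difference in composition could affect many regions in the same direction and look like a consistent biological pattern.

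The plan treats one non-inflammatory explanation, perfusion, seriously enough to add a scan for it. It has no analysis for composition, although the T1 scan it already collects would supply the data.

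**Working it through.** **1. The plan's own power figure.** Inputs from the Statistical Analysis Plan: d = 0.922, 20 per group, threshold 0.05. For a two-sided two-sample t-test, df = 38 and the noncentrality is 0.922 × √(20/2) = 2.916. Power is 0.811, which agrees with the stated 0.81. The same noncentral-t calculation is used below.

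**2. Voxel size.** 5.6 × 5.6 × 10 = 313.6 mm³. The T1 voxel is 0.9³ = 0.729 mm³, so one spectroscopy voxel covers about 430 T1 voxels (313.6 / 0.729).

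**3. What a CSF difference would do.** These inputs are assumptions; none is in the documents:
- mean ROI CSF fraction f of 10% or 15%;
- between-person coefficient of variation (CV) of 8%, 10% or 15%;
- a marker expressed as a concentration that scales with (1 − f);
- no true difference in tissue concentration.

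For a group difference Δ in CSF fraction, the relative shift is Δ / (1 − f), and the spurious effect size is d = shift / CV. The rejection rate is the two-sided noncentral-t probability at 20 per group.

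Examples at CV 10%:
- Δ = 3 points, f = 10%: 0.03 / 0.90 = 3.3%, d = 0.33, rejection 18%.
- Δ = 5 points, f = 15%: 0.05 / 0.85 = 5.9%, d = 0.59, rejection 44%.

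Full range over f = 10–15% and CV 8–15%:

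| Group difference in CSF fraction | Spurious d | Chance of p < 0.05 |
|---|---|---|
| 0 | 0 | 5% |
| 1 point | 0.07–0.15 | 6–7% |
| 2 points | 0.15–0.29 | 7–15% |
| 3 points | 0.22–0.44 | 11–27% |
| 5 points | 0.37–0.74 | 21–62% |

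**4. The stricter threshold.** If 0.0078 is read as a raw p-value cut-off, the rate with equal composition is 0.8%. At CV 10% it is about 5% for d = 0.33 and about 19% for d = 0.59. A stricter threshold lowers the rate but does not remove the bias.

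**5. Cost of one covariate.** With one tissue-fraction covariate, df falls from 38 to 37. At d = 0.922 and a covariate balanced between groups, power is 0.810 if the covariate is unrelated to the outcome within groups, 0.845 at a within-group correlation of 0.3, and 0.906 at 0.5. Imbalance between groups would lower these values.

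**6. Correcting the wrong marker.** CSF dilution largely cancels in a ratio of two metabolites. Dividing such a ratio by (1 − f) would itself create a group shift: 0.90 / 0.87 = 1.034 (+3.4%) when f goes from 10% to 13%, and 0.85 / 0.80 = 1.063 (+6.3%) when f goes from 15% to 20%. Any correction must therefore depend on how the marker is expressed.

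**The case against.** **Silence is not proof.** The documents describe no MRSI post-processing at all, so tissue correction may be one unstated step among many. This stands in part. A reader might infer that the T1 scan will be used for registration and nothing else, but the text names registration uses without excluding others. What the text supports is that no correction is planned in writing and that the stated test has no place for a covariate.

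**Voxels are not tested.** A reader might also take the t-tests to run on single voxels. They run on ROI values. This corrects the unit of analysis but leaves the bias, because ROI averaging keeps a systematic difference.

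**The mechanism does not cover every outcome.** The perfusion paragraph indicates that temperature is among the quantities of interest. The dilution argument concerns signal amplitude and does not carry over to temperature. Ratios largely escape dilution by CSF, though not a difference in the grey/white mix. Both limits stand.

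**The design already helps.** The shared age and body mass index range, common deployment and the exclusions make a large difference in composition less likely. They do not rule one out.

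**Adjustment may change the question.** If atrophy is part of the illness, adjusting for grey-matter fraction removes some of what the study seeks. This stands, and is a reason to keep the planned t-test and report both.

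**Conclusion.** The point holds as a gap in the planned analysis. Followed as written, the plan offers no way to tell a difference in CSF or grey-matter fraction from a neuroinflammatory difference in the metabolite markers, although it does address perfusion.

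Its size is unknown. A reader might infer that the groups do differ in composition, or that false-positive rates near the top of the table are expected. The documents support neither: they contain no data on tissue fractions, and with equal composition the per-test rate stays at 5%. The table is conditional on the assumed CSF fraction, CV and marker expression. It shows that a 1-point difference hardly matters, while 3–5 points would raise the rate to 11–62%.

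The plan's power statement is unaffected. This is an inexpensive improvement worth making.

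**What to change.** 1. State how each of the five markers is expressed: concentration, metabolite ratio or temperature.
2. Segment the existing T1 scan into grey matter, white matter and CSF, and resample the fractions to the MRSI grid.
3. Apply CSF-fraction correction only to markers expressed as concentrations, not to metabolite ratios or temperature.
4. For each metabolite marker in each ROI, report a linear model with group and ROI grey-matter fraction beside the planned t-test.
5. Do not describe a difference as neuroinflammatory beyond tissue composition unless it persists in the adjusted model.

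If the processing pipeline already corrects for tissue, write that step into the plan.

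**Cost.** Extra processing and analysis code, no new scan, and one degree of freedom per model (power 0.811 to 0.810 at d = 0.922 if the covariate is balanced and unrelated to the outcome). Some precision is lost if tissue fraction differs between groups. If atrophy lies on the disease pathway, the adjusted estimate answers a different question from the unadjusted one, which is why both are reported.

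### Does the mismatch between the T1 scan's field of view, matrix and stated voxel size call for a change to the plan?

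*Combined protocol and SAP*

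**What the plan says.** The T1 entry under Neuroimaging sequences in the Study Protocol states the purpose of the scan first: "For spatial registration, we will use a magnetization-prepared rapid gradient echo (MPRAGE) sequence". It then gives the geometry and the resulting voxel size together: "224mm FOV, 320 x 320 matrix, 2400ms TR, 2.15ms TE, 0.9mm slice thickness, and no gap, yielding a 0.9 x 0.9 x 0.9mm" image. The entry mentions no interpolation, rectangular field of view or resampling.

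Two other scans are specified in the same section. The whole-brain MRSI scan, which supplies the spectroscopic measures, has an "FOV of 280mm in-plane and 180mm in the inferior-superior direction to yield 5.6x5.6x10mm voxels". The arterial spin labeling (ASL) scan has 4 x 4 x 10 mm voxels; its images are co-registered to the T1 image and smoothed with a 6 mm kernel.

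The Statistical Analysis Plan compares the groups by independent-samples t-tests on five neuroinflammatory outcomes in 47 brain areas. It does not mention the T1 image.

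**The concern.** In-plane voxel size is field of view divided by matrix size. A 224 mm field on a 320 matrix gives 0.7 mm, yet the same sentence says 0.9 mm. Only the slice direction agrees. A reader cannot tell which of the four figures (field of view, matrix, slice thickness, voxel size) is wrong.

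If the T1 image is what places the 47 brain areas on the spectroscopic data, an ambiguous specification might let scans be set up differently from one participant to the next. That would add variation in the position of the regions. A group repeating the study from this document would also not know which setting to follow. By volume the discrepancy looks large: the implied voxel is 40% smaller than the stated one.

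**Working it through.** **Inputs** (all from Neuroimaging sequences)

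- T1: field of view 224 mm, matrix 320 x 320, slice thickness 0.9 mm without gap, stated voxel 0.9 x 0.9 x 0.9 mm.
- MRSI: field of view 280 mm in-plane and 180 mm inferior-superior, voxel 5.6 x 5.6 x 10 mm.
- ASL: voxel 4 x 4 x 10 mm.

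**Step 1. Try to reproduce the stated T1 voxel.**

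- In-plane size = field of view / matrix = 224/320 = 0.70 mm, against 0.9 mm stated. It does not reproduce.
- Through-plane size = slice thickness = 0.9 mm. It agrees.
- A 0.9 mm in-plane size would need a field of view of 0.9 x 320 = 288 mm, or a matrix of 224/0.9 = 248.9, about 249.
- It is also possible that 0.7 mm on every side was intended, with slice thickness and stated voxel both misprinted. The document does not decide between these.

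**Step 2. Check the convention on the MRSI line.** 280/5.6 = 50 and 180/10 = 18. Both are whole numbers, so field of view divided by matrix fits there. Only the T1 line fails.

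**Step 3. Size of the discrepancy in T1 voxels.**

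- Implied volume: 0.7 x 0.7 x 0.9 = 0.441 mm³.
- Stated volume: 0.9 x 0.9 x 0.9 = 0.729 mm³.
- Ratio: 0.441/0.729 = 0.605, so about 40% smaller.

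**Step 4. Size relative to the images registered or analysed.**

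| Image | Voxel volume | Divided by 0.729 mm³ | Divided by 0.441 mm³ | 0.2 mm as share of in-plane side |
|---|---|---|---|---|
| MRSI | 5.6 x 5.6 x 10 = 313.6 mm³ | 430 | 711 | 0.2/5.6 = 3.6% |
| ASL | 4 x 4 x 10 = 160 mm³ | 219 | 363 | 0.2/4 = 5.0% |

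The 0.2 mm is the difference in T1 voxel side (0.9 − 0.7). It is a difference in sampling fineness, not a displacement of the image, so the last column overstates any registration error.

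**Step 5. Trace the T1 figures into the analysis.** The power calculation uses d = 0.922, 20 per group and two-sided 0.05. With the noncentral t distribution on 38 degrees of freedom this gives 0.811, matching the plan's 0.81. No T1 setting enters that calculation, the t-tests or the FDR threshold.

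**The case for a change.** The best case for acting is that the error is certain and almost free to correct. The contradiction sits inside one sentence of continuous prose, rounding cannot bridge 0.70 and 0.9, and basing the settings on a published project does not make both figures true. The plan also aims to pick out differences likely to be replicable, so an acquisition line that cannot be followed as written is awkward. A methods section copied from it would carry the slip forward. All of this stands as a remark about reporting.

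The claims of harm within the study do not stand.

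- **Mixed set-up.** The document describes one named scanner in one laboratory and a single imaging session for each of the 40 participants. A wrong number in a summary is not evidence that scanner settings varied.
- **Placement of the 47 areas.** That the T1 image does this is a fair inference from its stated purpose, but the document does not describe how regions are transferred to the spectroscopic data. Even if the inference is right, Step 4 shows that either T1 resolution is far finer than the data being localised.
- **Resampling to equal sides before registration.** Nothing in the document requires it, and it does not follow from the mismatch.

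**Conclusion.** The arithmetic criticism is correct: the listed settings imply 0.7 x 0.7 x 0.9 mm, not 0.9 mm on every side. It is a clerical inconsistency, and no change to the plan follows. The image supports registration and is not an outcome; either candidate voxel is hundreds of times smaller by volume than the MRSI and ASL voxels; and no test, power figure or threshold depends on it. The 40% volume difference describes a supporting image and does not carry over to the measured quantities.

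This rests on two assumptions. First, the same sequence was run for all participants, as the single-scanner description suggests. Second, the analysis takes the image geometry from the stored scans and not from the protocol text, as is usual. On those terms anyone writing up the methods would read the true voxel size from the scan files, which would also show which figure slipped. Correcting the line would improve the record, but would not be expected to change any regional value, group comparison or conclusion.

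### Controls only have to share the cases' age and BMI range, and every comparison is an unadjusted t-test, so a systematic age or BMI difference can appear as a group difference in any marker that tracks it

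*Combined protocol and SAP*

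**What the plan says.** The Overall design section describes an observational comparison: "A cross-sectional approach is used to contrast 20 veterans with GWI from 20 veterans who were deployed to the Persian Gulf" without developing symptoms. Under Participants, the cases come mainly from an existing screening database, and for the controls the plan says "We have a database of individuals who served in Operation Desert Storm and do not present with symptoms of GWI". Comparability on age and BMI rests on one sentence: "Individuals will be within the same age and body mass index range as the GWI group". No individual or frequency matching, tolerance or balance check is given.

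The Statistical Analysis Plan says "Univariate, independent samples t-tests will be used to test for group differences for each brain marker" and region combination. There are five markers and 47 brain areas, plus whole-brain averages. It adds that "the main predictor of interest is group (GWI vs healthy"). The word main could suggest further predictors, but none is named and an independent-samples t-test cannot carry one. Results are reported at 0.05, and a second threshold is set: "we will use a false-discovery-rate (FDR) adjusted p-value of < 0.0078 to identify differences that are most likely to be replicable".

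No adjustment or sensitivity analysis for age or BMI appears anywhere. The perfusion scan under Neuroimaging sequences deals with blood flow only.

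**The concern.** Without randomisation, nothing makes the two groups' age and BMI distributions equal in expectation. Age and BMI are the only two characteristics on which controls are required to resemble cases, so the authors evidently consider them relevant. The analysis then uses neither.

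Chance imbalance alone is not the problem, because the t-test's overall error rate already allows for it. The problem is a systematic difference, for example one arising from how the two databases were filled. That adds a fixed bias to every marker and region that tracks the variable, and it can create a difference or hide one. If a marker tracks age in many regions, a single age difference moves them all in the same direction and can look like diffuse neuroinflammation. A consistent regional pattern would therefore not rule it out. A stricter p-value reduces the number of positives but leaves the bias in place, so biased contrasts could still be picked out as the ones likely to replicate.

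**Working it through.** **Inputs from the Statistical Analysis Plan.** The sample size and threshold are given as "with a statistical threshold of 0.05 and 20 individuals per group". The planning effect is d = 0.922, the stated power is 0.81, and the second threshold is 0.0078. The number of tests is 5 × 47 = 235, before the whole-brain averages.

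**Assumed inputs.** The documents give neither the within-group correlation r between marker and age nor the systematic age difference D in within-group SDs. Ranges are used for both.

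**1. The plan's own figure.** For a two-sided t-test with df = 38, the noncentrality is d × √(n/2) = 0.922 × √10 = 2.916 and the critical value is 2.024. Power is 0.811, which matches the stated 0.81.

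**2. Bias of the unadjusted test.** With no true group effect and a within-group marker SD of 1, the expected group difference is r × D. The false-positive rate is the power of the t-test at noncentrality r × D × √10. For example, r = 0.5 and D = 0.5 gives 0.25 × 3.162 = 0.791 and a rate of 0.12. The 0.0078 column treats that value as a nominal cut-off.

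| D (SD) | r | Spurious d | Rate at 0.05 | Rate at 0.0078 |
|---|---|---|---|---|
| 0.25 | 0.2 | 0.05 | 0.053 | 0.0085 |
| 0.25 | 0.3 | 0.075 | 0.056 | 0.0094 |
| 0.5 | 0.3 | 0.15 | 0.075 | 0.015 |
| 0.5 | 0.5 | 0.25 | 0.12 | 0.029 |
| 0.7 | 0.3 | 0.21 | 0.10 | 0.022 |
| 0.7 | 0.5 | 0.35 | 0.19 | 0.054 |

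Simulating the model with group, age and BMI in these settings (40,000 replicates each) gives a rate of about 0.05 throughout.

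**3. Does the range rule prevent such differences?** Ages were drawn from bounded beta distributions, and controls were redrawn until they lay inside the observed range of the cases (20,000 replicates).

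| D before rule | D after rule | Reduction | t-test rate, r = 0.3 | t-test rate, r = 0.5 |
|---|---|---|---|---|
| 0.82 | 0.68 | 1 − 0.68/0.82 = 17% | 0.10 | 0.18 |
| 0.63 | 0.53 | 1 − 0.53/0.63 = 16% | 0.08 | 0.13 |
| 0.47 | 0.38 | 1 − 0.38/0.47 = 19% | 0.06 | 0.09 |

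The reductions are worked from rounded shifts and depend on the shapes chosen (the first row uses beta(2,2) for cases and beta(2,4) for controls). They show that the rule can leave most of a difference in place. They do not show that a difference exists.

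**4. What adjustment does to precision and power.** The model has df = 36. The ratio of its standard error to the t-test's is 0.98 (r = 0.3) and 0.89 (r = 0.5) with balanced groups, 1.01 and 0.92 at D = 0.5, and 1.04 and 0.94 at D = 0.7. Power at d = 0.922, against 0.81 for the t-test, is as follows:

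- Neither covariate matters, groups balanced in expectation: 0.79. With exactly equal sample means it would be 0.810, and the gap is the cost of chance imbalance.
- Neither matters, but one differs by 0.5 to 0.7 SD: 0.76 to 0.74. If both differ: 0.74 to 0.69.
- Age tracks the marker, groups balanced: 0.83 (r = 0.3) or 0.89 (r = 0.5).
- r = 0.3 with an age difference of 0.5 to 0.7 SD: 0.80 to 0.78.

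**The case against.** The best defence is that the design already deals with much of this. Both groups served in the same conflict, major cardiovascular illness and cancer are excluded in both, and age and BMI are restricted. Nothing in the documents shows that the groups differ, and the range simulation starts from a difference that was put in by assumption. With a modest remaining difference of 0.38 SD the rate is only 0.064 at r = 0.3 and 0.056 at r = 0.2. This stands as a limit on the size of the problem. It does not remove the gap, because the plan neither adjusts for a difference nor provides a check that would reveal one.

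The exploratory label is a weaker defence. The plan uses it to justify its handling of multiplicity, which is a different matter from confounding, although it does lower the stakes of any single biased contrast.

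The rates at 0.0078 hold only if that value is a nominal cut-off. If it applies to FDR-adjusted p-values, those figures do not carry over, but it remains true that no threshold removes a bias.

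Finally, BMI may be a consequence of the illness, in which case adjusting for it could remove part of the effect of interest. The documents do not settle this. The plan already conditions on BMI by restricting its range, so a model that includes it is consistent with the design, but an age-only model must be shown beside it.

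**Conclusion.** The concern holds. Range-only comparability in a non-randomised study, combined with group-only t-tests, leaves any systematic age or BMI difference in every contrast that tracks it. The size is unknown. Under the assumed correlations and differences, the per-test false-positive rate at 0.05 runs from a negligible 0.053 to 0.19. The largest spurious effect considered, 0.35 SD, is 0.35/0.922 = 38% of the planning effect. These figures assume a linear marker-age relation and a systematic difference, and the documents neither support nor exclude such a difference. Confidence in the practical importance is moderate. The change is inexpensive and should be made, but the point does not invalidate the study.

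**What to change.** Prespecify a linear model for each marker and region with group, age and BMI as terms. Report the adjusted group difference with its 95% confidence interval, and tabulate age and BMI by group. Keep two sensitivity analyses: the unadjusted t-test as now planned, and a model with age only to cover the possibility that BMI is a consequence of illness.

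The change is to SAP wording and one model line. No new data are needed, because age and BMI must be known to apply the range rule. It costs 2 degrees of freedom (36 rather than 38). The price in power is real if the covariates do not predict the markers: 0.79 with balanced groups and 0.69 in the least favourable case examined. If age does predict the marker and the groups are balanced, power rises above the planned 0.81.
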